---

## LIST OF TABLES

Table 1: Schedule of Events (Season 1, 2018) (Cohort 1).....	15
Table 2: Schedule of Events (Season 2, 2019) (Cohort 2).....	17
Table 3: Quantitative Systemic Reactogenicity Grading.....	24
List of abbreviations	

---

Abbreviation special term	or Explanation
AE	Adverse Event/Adverse Experience
AESIs	Adverse Events of Special Interest
CDC	Center for Disease Control
CMI	Cell-mediated immunity
CRO	Contract Research Organization
Ct	Cycle threshold
DSMB	Data and Safety Monitoring Board
ICF	Informed Consent Form
IIV	Inactivated influenza vaccine
IIV3	Trivalent inactivated influenza vaccine
ILI	Influenza-like illness
ITT	Intent-to-treat
M-001	Multimeric-001
MedDRA ®	Medical Dictionary for Regulatory Activities
N	Number (typically refers to subjects)
NOCI	New Onset of Chronic Illness
NP	Nasopharyngeal
PBMC	Peripheral Blood Mononuclear Cell(s)
PBS	Phosphate Buffered Saline
PCR	Polymerase Chain Reaction
PP	Per-Protocol
PT	Preferred Term
qRT-PCR	Quantitative Reverse Transcriptase Real Time PCR
SAE	Serious Adverse Event/Serious Adverse Experience
SOP	Standard Operating Procedure
SOC	System Organ Class
TBD	To be determined later
US	United States
VE	Vaccine Efficacy
WHO	World Health Organization

---

## **OVERVIEW AND SUMMARY OF CHANGES FROM STATISTICAL ANALYSIS PLAN FINAL 1.0 DATED 17 DECEMBER 2018**

The SAP version 1.0 approved on December 17, 2018 is updated to version 2.0

- to incorporate changes made to the protocol through the current version 5.0 - Amendment 1.0 of the protocol,
- to add analyses missing in SAP version 1.0 to be in line with the protocol,
- to describe some conventions following a blinded data review meeting that took place after the end of flu season 2018-2019,
- to clarify one exploratory endpoint, add 2 exploratory endpoints and 2 sensitivity analyses, and
- to incorporate some editorial changes.

Updates to the SAP version 1.0 related to protocol amendment concern:

- the change to the study design with the addition of a second cohort to reach a total of ~12,000 subjects in the study. The second cohort is evaluated during the flu season 2019-2020 while cohort 1 was evaluated during the flu season 2018-2019 (section 3.4). In addition, no subject was participating in two consecutive flu seasons.
- the removal of the long-term efficacy assessment over a second influenza season from the list of secondary objectives. All efficacy and safety analyses related to second flu season were removed from SAP version 1.0 (section 2.2).
- the addition of an immunogenicity objective (section 2.2) and immunogenicity endpoints in section 6.
- the removal of the exploratory objective 2. in SAP version 1.0 concerning the assessment of incidence of clinic visits associated with the ILI episode
- the presentation of safety and efficacy results by cohort (cohort 1 and 2, corresponding to flu season 2018-2019 and 2019-2020, respectively)
- the removal of fever from the list of solicited symptoms. Presence/absence of fever will be evaluated using the reported temperature by the subject (Section 4.1)

The following updates were made to the first version of SAP to be in line with the protocol version 5.0 (these analyses were missing from SAP version 1.0 but are described in the protocol):

- the addition of statistical comparisons between the 2 groups in terms of percentage of subjects with any local or systemic reactogenicity solicited events overall and by vaccination (as specified in the protocol). Within-group comparisons between the percentage of subjects with any local or systemic reactogenicity solicited events after first and second vaccination are specified. The 95% exact CI for the proportion of subjects with unsolicited AEs by SOC and PT will be presented. Within group 95% CI for the proportion

of subjects with serious SAEs will be derived using the exact method by SOC, PT (section 4.4).

- the addition of the analysis comparing the proportion of subjects with ILI symptoms, in addition to the analysis comparing the rate of ILI symptoms over one year (section 5.4.2 – secondary efficacy endpoints)

The following updates were made to the first version of SAP following blinded review of data from season 1:

- the ILI episode for which a nasal or throat swab was collected outside of the allowed window of 3 days post onset date will be considered as a qRT-PCR or culture confirmed ILI if the results of the qRT-PCR or culture are positive. Review of each case will be performed prior to unblinding and documentation provided in the blinded data review meeting memo (see section 5.3).
- the analysis of the secondary efficacy assessment consisting in the between-group comparison of the number of days with respiratory or systemic symptoms among subjects with qRT-PCR- or culture-confirmed influenza illness will be performed on the percentage of subjects with number of days with respiratory or systemic symptoms in the following categories:
  - < 7days
  - At least 7 and < 14 days
  - At least 14 and < 21 days
  - $\geq 21$  days

Cochran-Mantel-Haenszel test with 4 strata corresponding to the combination of age category and cohort will be used.

Clarification of the exploratory analysis :

- Influenza virus subtype in the swab samples to compare the viruses causing disease in the experimental vs control group

To read:

- Percentage of either qRT-PCR or culture-confirmed influenza cases in the M-001 experimental group vs. placebo by virus type (influenza A and B) and Influenza A subtypes (H1N1 and H3N2) as well as Influenza B lineage (B/Yamagata and B/Victoria ).

Additional exploratory analyses:

- Reduction, due to vaccination with M-001, in the proportion of subjects with serious ILI with or without confirmation by viral culture or qRT-PCR analysis
- Reduction, due to vaccination with M-001, in the proportion of subjects taking medications due to qRT-PCR- or culture-confirmed ILI

An additional sensitivity analysis for the primary efficacy assessment is added in section 5.4.2. where the following definition is used: influenza is confirmed by a qRT-PCR or culture if the qRT-PCR Ct count corresponding to the detection of any flu type is < 40 or culture is positive for influenza.

An additional sensitivity analysis to the secondary efficacy assessment of proportion of subjects with ILI is added in section 5.4.2. where selection of ILI which occurred prior to March 15th, 2020 will be done.

The following updates made to the first version of SAP are provided for clarity or are editorial:

- section 3 of SAP version 1.0 has been extended to present the study outcome measures as defined in the protocol
- section 4.4 : To match the primary safety objective related to occurrence of unsolicited AEs from the time of first study vaccination through 22 days after each M-001 vaccination (day of the vaccination inclusive), selection of unsolicited AEs will be performed using the cut-off of 22 days after each M-001 vaccination (instead of the 30 days cut-off in SAP version 1). Safety tables reporting all AEs irrespective of the time will be provided also
- the criteria for exclusion from the PP set reported in section 5.3 were clarified.
- section 7 of SAP version 1.0 on handling of missing data is now section 9
- section 8 of SAP version 1.0 on subgroup analysis is now section 7, more details on subgroup analyses are provided in version 2.0.
- section 9 of SAP version 1.0 on assessment of study population has been extended to include section 10 of SAP version 1.0 and is section 8 in version 2.0
- new section section 8.2.1 has been added in SAP 2.0 to define Medical History reporting.
- new section section 8.2.2 has been added in SAP 2.0 to define prior medication and concomitant medication selection and reporting.
- section 11 of SAP version 1.0 is section 10 in version 2.0
- section 12 of SAP version 1.0 on interim analyses and data monitoring committee was removed. Section 12 in the SAP version 2.0 presents the tables, figures, and listings to be provided
- section 13 of SAP version 1.0 on changes of analysis from protocol is section 11 in version 2.0

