11.5.2. Analysis of Safety Data

Summaries and analysis of safety data will be presented for the Safety Analysis Population.

Solicited events will be summarized by severity for each day after each study vaccination (Days 0-7 post each study vaccination, 8 days in total) and as the maximum severity over all 8 days (day of the vaccination inclusive). Additionally, solicited events will be analyzed by taking the most severe response over the follow-up period and using standard techniques, such as exact confidence intervals, to summarize the proportion of subjects reporting each symptom, any injection site symptom, and any systemic symptom. Summaries of solicited events will be presented separately for each study vaccination as well as overall study vaccinations by treatment arm. The proportion of subjects reporting symptoms may be compared between treatment arms using Chi-square or Fisher's exact test, as appropriate. The proportion of subjects reporting solicited symptoms between the different study vaccinations (e.g., dose 1 vs. dose 2) will be compared using McNemar's test.

Unsolicited AEs will be coded by Medical Dictionary for Regulatory Activities (MedDRA[®]) for preferred term and system organ class (SOC). The number of SAEs is expected to be small in this trial and SAEs will be reported by detailed listings showing the event description, MedDRA[®] preferred term and SOC, relevant dates (study vaccinations and AEs), severity, relatedness, and outcome for each event. Non-serious unsolicited AEs will be summarized as number and percentage of subjects reporting at least one event in each MedDRA[®] preferred term and SOC, cross tabulated by severity and relationship to study product. Additionally, the proportion of subjects and exact 95% confidence intervals of AEs in aggregate and by MedDRA[®] categories will be computed.

Graphical presentations may include box plots and shift plots.

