### 4.4 Safety Endpoints Analysis

#### Local and Systemic Reactogenicity Events – Overall Summaries

Each set of tables described below will summarize the occurrence of events over the 3 following periods:

- P1. any day over 8-day period following first or second vaccination (Period = Day of the first/second vaccination to 7 days post first/second vaccination)
- P2. any day over 8-day period following first vaccination (Period = Day of the first vaccination to 7 days post first vaccination)
- P3. any day over 8-day period following second vaccination (Period = Day of the second vaccination to 7 days post second vaccination)

Summary of all the local and systemic reactogenicity **solicited** events provided for

- any local or systemic reactogenicity solicited events,
- any local events and by local event separately (5 events: blue spot/bruising, induration/swelling, redness/warmth, itching, pain/tenderness),
- any systemic reactogenicity events and by systemic reactogenicity event separately (14 events: decreased blood pressure/dizziness, chills/sweating, joint/muscle pain, headache, nasal congestion/runny nose/phlegm production/rhinitis, difficulty breathing/wheezing, general malaise/fatigue/loss of appetite, swelling/tender lymph nodes, irritability, rash, cough, sore throat, abdominal pain/diarrhea/nausea/vomiting, pruritus or itching on the body).

During the first season, fever was one of the solicited symptom and was graded subjectively as mild, moderate, or severe by the subject in addition to the oral body temperature daily record. This symptom was not recorded as such during the season 2019-2020. For homogeneity of reporting, oral body temperature daily records only will be presented for the 2 seasons and a separate table summarizing fever as a solicited symptom will be presented for season 2018-2019.

The tables will present the number and percentage of subjects with any events, the percentage in each table being computed using the number of subjects having received the specified vaccination and with diary data reported for local and systemic reactogenicity in the period of interest as defined in P1, P2, and P3.

For each of the above tables, the number and percentage of subjects will be tabulated by treatment.

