The percentage of subjects with any local or systemic reactogenicity solicited events overall and by vaccination will be compared between the groups using the chi-square test. Within-group comparison between the percentage of subjects with any local or systemic reactogenicity solicited events after first and second vaccination will be performed using Mc Nemar test.

Descriptive tables for duration of event will also be provided by solicited event.

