### **Recorded Temperature by Severity – Overall Summary**

A table summarizing the grading of the temperatures will also be provided using the temperatures recorded by the subject during the 8-day post first, second and first or second vaccination. Temperature will be graded as in Table 3.

The severity, which is missing for an event, will remain missing in the analysis.

The percentage of subjects with temperature overall and by vaccination will be compared between the groups using the chi-square test. Within-group comparison between the percentage of subjects with temperature after first and second vaccination will be performed using Mc Nemar test.

Table 3: Quantitative Systemic Reactogenicity Grading

Systemic (Quantitative)	Mild (Grade 1)	Moderate (Grade 2)	Severe (Grade 3)
(Age <60 years) Fever - oral	38.0°C – 38.4°C	38.5°C – 38.9°C	>38.9°C
(Age ≥60 years) Fever - oral	37.3.0°C – 37.7°C	37.8°C – 38.2°C	>38.2°C

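### The SAP tests solicited reactogenicity between arms only as a pooled local-or-systemic outcome (temperature apart) and omits the confidence intervals the protocol suggests for each symptom, any injection-site symptom and any systemic symptom

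*SAP*

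**What the plan says.** Protocol 3.2.1 and SAP 3.1 both list solicited injection-site and systemic events among the primary safety outcomes.

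Protocol 11.5.2 takes each subject's most severe response and proposes "using standard techniques, such as exact confidence intervals, to summarize the proportion of subjects reporting each symptom, any injection site symptom, and any systemic symptom". It then adds a permissive sentence on testing: "The proportion of subjects reporting symptoms may be compared between treatment arms using Chi-square". Fisher's test is the stated alternative. It names no outcome that combines local and systemic symptoms.

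SAP 4.4 (Local and Systemic Reactogenicity Events – Overall Summaries) has three separate bullets: the pooled local-or-systemic outcome; "any local events and by local event separately" (five local events); and any systemic event with 14 systemic events separately. The tables give number and percentage by treatment, over both doses and after each dose. The inference sentence reads: "The percentage of subjects with any local or systemic reactogenicity solicited events overall and by vaccination will be compared between the groups". The method named is chi-square, with McNemar's test for dose 1 against dose 2 within arm. For recorded temperature there is a further test: "The percentage of subjects with temperature overall and by vaccination will be compared between the groups using the chi-square test".

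The overview entry for this change reads "the addition of statistical comparisons between the 2 groups in terms of percentage of subjects with any local or systemic reactogenicity solicited events overall"; it describes the new comparison as what the protocol specifies. SAP section 11 (Changes of Analysis from Protocol) does not mention solicited events. In the SAP table list, interval tables are titled for SAEs (14.2.13.8) and for adverse events by SOC and preferred term (14.2.17.2 and 14.2.17.9). No solicited-event table (14.2.15.x) is titled with one.

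**The concern.** Version 2.0 of the SAP was revised partly to add protocol analyses that version 1.0 lacked. Protocol 11.5.2 mentions exact intervals twice, once for solicited events and once for adverse events. The SAP took up the second and not the first, without saying so.

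The wording of the between-arm test matches the pooled bullet. That outcome mixes injection-site reactions with headache, fatigue, joint or muscle pain, cough and nasal symptoms, which people aged 50 and over can have in any 8-day period without vaccination. A subject with one of these already counts as an event, so a vaccine-caused local reaction in that subject adds nothing. The local difference shrinks and the background rate rises.

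At stake is how well a pivotal trial describes its reactogenicity. A non-significant pooled result would say little about small local effects. A significant one would not say whether local or systemic events cause it. At neither level is there a planned interval to show the size of a difference.

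**Working it through.** **Plan's own figure.** The documents give no rate, power or sample size for solicited reactogenicity, so there is nothing to reproduce.

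**Inputs.** About 6,000 subjects per arm (Protocol section 4). This slightly flatters the power, because the SAP's denominator is subjects with diary data. Two-sided 5% level (my assumption for the chi-square test; SAP 10.1 makes no multiplicity adjustment). Assumptions not in the documents: systemic rate *s* of 30%, 40% or 50%, equal in both arms; local rate *l* as shown; local and systemic reactions independent.

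**Formulas.** Pooled rate = 1 − (1 − s)(1 − l). The pooled difference is therefore (1 − s) times the local difference. Power ≈ Φ(|p₁ − p₀| / SE − 1.96), with SE = √{[p₀(1 − p₀) + p₁(1 − p₁)] / 6000}.

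**Example: local 5% v 7%.**
- Alone: SE = √{(0.05×0.95 + 0.07×0.93)/6000} = 0.00433; 0.02/0.00433 − 1.96 = 2.66; power 99.6%.
- Pooled, s = 40%: 1 − 0.6×0.95 = 43.0% and 1 − 0.6×0.93 = 44.2%; difference 1.2 points; SE = 0.00905; 0.012/0.00905 − 1.96 = −0.63; power 26%.

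**Results.**

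| Local rate, placebo v M-001 | Power alone | Pooled, s = 30% | Pooled, s = 40% | Pooled, s = 50% |
|---|---|---|---|---|
| 5% v 7% | 99.6% | 37% | 26% | 19% |
| 10% v 12% | 94% | 35% | 26% | 20% |
| 10% v 15% | >99% | 98% | 91% | 79% |
| 10% v 20% | >99% | >99% | >99% | >99% |

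For 10% v 20%, a doubling of local reactions, the pooled rates at s = 30% are 37% v 44% (ratio 0.44/0.37 = 1.19). At s = 50% they are 55% v 60% (ratio 0.60/0.55 = 1.09). The test is significant but conveys little about the local effect.

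**Departure from independence.** If 70% of the excess local reactors also have a systemic event, only 0.3 of the excess reaches the pooled outcome. For 10% v 15% that is 0.3 × 5 = 1.5 points, and pooled power falls to about 40% (s = 30%) or 38% (s = 40%).

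**What separate intervals would give.** The half-width for a between-arm difference is about 1.96√{2p(1 − p)/6000}: 0.4 points at p = 1% and 1.8 points at p = 40%. The trial can size these differences precisely.

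**The case against.** Several points on the other side stand.

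- **Permissive protocol wording.** Exact intervals are given as an example and the between-arm test is optional. A reader might infer that the SAP breaks a firm requirement. It does not: it leaves out a suggested technique and narrows an optional comparison. The protocol's intervals are also for proportions within each arm, so omitting them does not remove a between-arm test.
- **Not the only between-arm test.** Temperature is tested too, and the symptom test is run overall and after each dose. None of this addresses injection-site reactions on their own.
- **Ambiguous sentence.** The phrase in SAP 4.4 could mean two tests, one local and one systemic. The first-versus-second-dose tables (14.2.15.13 to 14.2.15.15), which serve a comparison described in the same words, are organised by symptom and intensity. The separate bullets favour the pooled reading, but the text does not settle it.
- **Some intervals exist.** Solicited events that were also recorded as adverse events enter the adverse-event tables, some with exact intervals. Under SAP 4.1 these are the severe, medically assisted or persisting ones, so mild and transient reactions are not covered.
- **Nothing is hidden.** Counts by arm are planned for any local event and each local symptom, in each period and by grade, and tables 14.2.15.1 and 14.2.15.4 are top-line. A reader might infer that a clear local excess would go unseen; these tables rule that out.

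The SAP's only formal efficacy hypothesis concerns vaccine efficacy, and section 10.1 treats everything else as supportive. That limits the weight of any safety p-value, but it is no reason to leave out descriptive intervals.

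**Conclusion.** The concern holds in a limited form. For a primary safety outcome, the SAP provides no intervals at the three levels the protocol names. It most naturally tests the symptoms only as a pooled outcome, and it neither declares the difference in section 11 nor describes it accurately in the overview.

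The practical loss is in detecting small local excesses formally, and in locating and sizing any difference. Under independence and the assumed rates, excesses of about 2 points would probably be missed by the pooled test, a 5-point excess would usually be found, and a 10-point excess almost always. Strong overlap between local and systemic reactions would extend the loss to 5-point excesses. All of these figures rest on background and local rates that the documents do not give.

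The stronger conclusion, that a real local-reaction problem would go unnoticed, is not supported. This is a change that should be made, not a flaw that undermines the safety assessment.

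**What to change.** In SAP 4.4:

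1. Add exact 95% confidence intervals by arm for each solicited symptom, any injection-site symptom and any systemic symptom.
2. State that the between-arm comparison is made separately for any injection-site symptom and for any systemic symptom, after each dose and overall. Report the M-001 minus placebo difference with its 95% interval, labelled descriptive. The stratified Newcombe method already used in SAP 5.4.2 would serve.
3. Keep the pooled local-or-systemic outcome as an additional line.
4. Correct the overview's statement that the comparison follows the protocol, or list any remaining departure in section 11.

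Between-arm intervals for every single symptom are optional: 19 symptoms over three periods would be 57 further unadjusted intervals.

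The cost is SAP wording and extra columns in tables already planned, with no new data. The downside is more unadjusted intervals, which the descriptive label handles.

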## 1. INTRODUCTION

This study compares the safety and clinical efficacy of M-001, an influenza vaccine administered intramuscularly twice in older adults and the elderly ( $\geq 50$  years of age) versus placebo.

The M-001 vaccine is produced as a recombinant protein in *E. coli*. In the current study, the vaccine is intended to be administered in a non-adjuvanted formulation at a 1 mg/dose level that has been found to be safe and immunogenic in previous clinical trials performed by BiondVax.

### 1.1 Background

Influenza is a common acute viral respiratory illness. Influenza is the eighth leading cause of death in the western worldi resulting in worldwide death toll of 250,000-500,000 annuallyii. The continued emergence of novel influenza A viruses in humans including pandemic subtypes underscores the need for focused efforts to prepare for the next influenza pandemiciii since each emergence of a new subtype of influenza virus in the human population has the potential to result in a global public health emergency.

Increased morbidity and mortality of elderly individuals from influenza infections poses a major medical and public health concern. US CDC estimated the seasonal influenza vaccine effectiveness during the 2004–17 season to be only 40% among the general populationiv and much lower among the elderlyv. Even when most circulating flu viruses are well matched to the flu vaccine the vaccine can reduce the risk of flu illness by between 40-60% among the overall population during seasonsvi.

Use of influenza vaccines is the primary means for preventing influenza. Current licensed inactivated vaccines are good for preventing influenza but are less effective than desired. In general, the older age group is more vulnerable to the disease and its complications due to concomitant medical conditions and a senescent immune system. People's immune system becomes weaker with age, placing people 65 years and older are at high risk of serious flu-related complications. Accordingly, elderly individuals are also less responsive to the seasonal vaccine and particularly susceptible to other strains that are not incorporated in the seasonal vaccinevii viii. It is estimated that 70-85% of flu-related deaths in the US have occurred among this age group posing a more effective influenza vaccine as a very large unmet medical need. Similar findings were observed in Europe, where the European monitoring of excess mortality for public health action (EuroMOMO) network ([www.euromomo.eu](http://www.euromomo.eu)) monitors weekly 'real-time' all-cause age-specific excess mortality in countries in Europe through a standardized approach, allowing pooling of results. It is expected that a winter season with predominance of influenza A(H3N2) has higher mortality impact on the elderly than a season with predominant influenza A(H1N1) or a season with low influenza A transmissionix. The reasons for that are that (1) influenza A(H1N1)pdm09 has less impact on the elderly and (2) since 2009 this strain is contained in the seasonal vaccine. Whereas current vaccines focus on enhancement of humoral immunity against the virus, it is known that cellular immunity also can have a role in preventing influenza-associated illnessx.

An approach to improve vaccine efficacy especially in the older adults and elderly is the use of a broadening vaccine that enhances cellular immunity against multiple influenza viruses (a universal vaccine) and that might also prime serological responses to influenza antigens.

